Posters displayed on admitting wards notify parents and patients that the centre is participating in a national service evaluation of children's bone and joint infections. Parents will have the opportunity to inform a member of their child's care team if they do not want their child's information entered into the database.

Sample size calculations

The study is funded to enable a maximum of 1,000 cases of OM or SA to be entered into the database. In order to get an accurate national evaluation, all participating centres will be asked to record cases for at least six months. It is estimated that at least 500 cases will be accrued by around 50 centres over a 6-12 month period. All eligible cases at participating centres will be recorded.

Data Collection

We will record demographic details and details of hospitalisation(s) including transfers between hospitals; type and site of disease; routine haematology, biochemistry and microbiology; radiological procedures; surgical procedures; length of IV therapy; antimicrobials used, route and duration; reason/criteria; used for oral switch (if any); and clinical outcomes at 3 months.

These data are to be collected from the patients' clinical notes. Training will be provided for teams at participating centres. The study will use a password protected web based data collection form that can be accessed at all participating hospitals.

Study Objectives

The study has three major objectives:

1. What are the clinical, biochemical and radiological criteria used by UK paediatricians / orthopaedic surgeons / radiologists to diagnose osteomyelitis?
2. What is the range of durations of intravenous and oral antibiotics used to treat osteomyelitis? What factors affect durations (e.g. surgery / blood tests / microbiology results).
3. What are the rates of treatment failures / complications for different:
 - (a) Antibiotic regimes used at participating centres?
 - (b) Surgery types used at participating centres?

and what actions were taken following a complication at participating centres?

These objectives are broken down into further sub-objectives:

- 1A:** Describe the study sample: demographics; past medical history; presenting limbs/joints affected; and diagnosis types aiming to identify factors predisposing children to bone and joint infections. Describe pre-presentation variables that affect drug choice, dosage and duration, in particular age, allergies and co-morbidities.

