- [2G] Antibiotics prescribed at discharge will be summarised using frequencies and percentages. There are a large number of antibiotics that could be prescribed by either

route. Of these, 4 named IV antibiotics and 5 named oral antibiotics are of particular interest. A category labelled ‘other’ will be used to define all other antibiotics given by each route. For each antibiotic and route, summary statistics will be reported for whether it was given at least once; daily dose per kg weight of child; and planned duration of course. This will give an overview of the most commonly planned antibiotic regimes at discharge [see Table 2F-1].

[2H] Antibiotic regimes post discharge are not always adhered to. The number and percentage of those stopped early will be reported, split by who took the decision (Parent / Hospital / GP). In the same way the number and percentage of patients who had a change to the planned regime will be reported split by who made the change (Hospital / GP). The frequencies of 5 possible reasons for shortening or changing regime will be explored [see Table 2G-1].

Objective 3

[3A] The number and percentages of cases experiencing a complication of any kind will be reported. These will be further split by ‘Complication Type’, and cross-tabulated with ‘Action Taken’ (None / Surgery / Change of antibiotic regime / Re-admission to hospital / Other) [see Table 3A-1].

[3B] Treatment failure is determined by complications that result in certain actions. e.g. Surgery. The outcomes ‘Treatment Failure’ (Y/N) and ‘Any Complication’ (Y/N) will be cross-tabulated with three antibiotic regime variables: Timing of oral switch (Early / Standard); Total course of antibiotics (Shortened / Standard); and Overall dose (High / Normal). Associations between regime types and outcomes will be measured using odds-ratios and 95% CIs. This will give an overview of whether treatment failure and complications may be more likely for certain types of regime [see Table 3B-1].

[3C] Treatment Failure (Y/N) and Any Complication (Y/N) will be cross-tabulated with surgery undertaken (limited to surgery post presentation). Associations between surgery types and outcomes will be measured using odds-ratios and 95% CIs. This will give an overview of whether treatment failure and complications may be more likely for certain types of surgery [see Table 3C-1].

Analyses of missing data / withdrawals

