As this is a service evaluation, there should be only a small number of withdrawals. Those that do occur will be documented. It may be of importance if withdrawals are clustered by centre.

Missing data will be noted and wherever possible, the reasons reported. If a large amount of data critical to the analysis are missing, some changes to the analysis plan may be needed.

Setting results in context of previous research

Once the service evaluation has been completed the results will be set in context of the existing evidence base.

References

2. ICH E3 chapter 12.

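### Objective 3 pools children from about 50 centres in crude odds ratios without saying how centre is handled, so the intervals may be too narrow and centre differences may mix with regime or surgery effects

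*SAP*

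**What the plan says.** Under Analysis, Objective 3, [3B] cross-tabulates Treatment Failure and Any Complication with timing of oral switch, total course and dose: "Associations between regime types and outcomes will be measured using odds-ratios and 95% CIs". [3C] uses the same method for surgery: "Associations between surgery types and outcomes will be measured using odds-ratios and 95% CIs". Tables 3B-1 and 3C-1 have columns for Yes, No and the odds ratio, and nothing for centre or centre type.

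On the number of centres, Sample size calculations states: "It is estimated that at least 500 cases will be accrued by around 50 centres over a 6-12 month period". It also gives a ceiling: "The study is funded to enable a maximum of 1,000 cases of OM or SA to be entered into the database".

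On the outcome, [3B] states: "Treatment failure is determined by complications that result in certain actions. e.g. Surgery". Study Objectives, objective 3, asks about failure rates by "Antibiotic regimes used at participating centres".

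Centre type does appear elsewhere. Several Objective 1 and 2 analyses are split Tertiary / Secondary, and Table 2A-2 applies that split to the three regime variables later used in [3B]. Clustering by centre is mentioned once, for withdrawals only: "It may be of importance if withdrawals are clustered by centre".

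**The concern.** A crude odds ratio with an ordinary 95% CI treats every child as independent. Two things can go wrong when children come from many hospitals.

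- **Precision.** If both regime and outcome are more alike within a centre than between centres, the interval is too narrow.
- **Bias.** If centres that favour one regime also tend to have higher or lower outcome rates for other reasons, the pooled odds ratio mixes the two. For example, centres that switch early and seldom act on a complication would make early switching look protective. This action-threshold route affects Treatment Failure. It does not affect Any Complication, which is not defined by an action.

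The SAP gives reason to expect variation between centres. Its Study Aim says there is little agreement on route or duration of treatment, and it sets out to measure practice in secondary and tertiary care. The result also has a use: the second aim is to judge whether a trial of shorter intravenous therapy is feasible, and early against standard switch is the first comparison in Table 3B-1.

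**Working it through.** **Inputs from the SAP.** About 50 centres, at least 500 cases, maximum 1,000. So 500/50 = 10 and 1,000/50 = 20 cases per centre on average. The main analysis takes simple cases only, so the average there is below 10 at 500 cases. That share is not given; 7 per centre is used below as an illustration.

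**Not in the SAP, so assumed.** ICCs of regime and outcome, event rate, exposure split, and the correlation between centre preference and centre outcome rate. The SAP states no power, precision or design effect to reproduce.

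**Step 1: interval width.** When exposure can vary within a centre, the design effect is about

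DE = 1 + (m − 1) × ICC(regime) × ICC(outcome)

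with m cases per centre. Coverage of a nominal 95% CI is 2Φ(1.96/√DE) − 1. For m = 10, ICC(regime) 0.5 and ICC(outcome) 0.10: DE = 1 + 9 × 0.5 × 0.10 = 1.45, √DE = 1.20, coverage 89.6%. With equal centre sizes:

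| ICC regime | ICC outcome | DE (coverage), m = 7 | m = 10 | m = 20 |
|---|---|---|---|---|
| 0.2 | 0.05 | 1.06 (94.3%) | 1.09 (94.0%) | 1.19 (92.8%) |
| 0.2 | 0.10 | 1.12 (93.6%) | 1.18 (92.9%) | 1.38 (90.5%) |
| 0.5 | 0.05 | 1.15 (93.2%) | 1.23 (92.3%) | 1.48 (89.3%) |
| 0.5 | 0.10 | 1.30 (91.4%) | 1.45 (89.6%) | 1.95 (84.0%) |
| 1.0 (centre fixes regime) | 0.10 | 1.60 (87.9%) | 1.90 (84.5%) | 2.90 (75.0%) |

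Unequal centre sizes raise these values. With a coefficient of variation of 0.8, m = 10 acts as 10 × (1 + 0.8²) = 16.4, and the first four rows become 1.15, 1.31, 1.39 and 1.77. If either ICC is near 0, DE is near 1.

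**Step 2: bias.** Simulation: 50 centres of 10 children, 10% failure, 50% early switch, true within-centre odds ratio 1, 3,000 runs per setting. ICCs here are on the latent logistic scale, so they do not match the table row for row.

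| Centre-level correlation | Latent ICC regime, outcome | Mean crude OR | Coverage |
|---|---|---|---|
| 0 | all six settings | 0.996 to 1.006 | 93% to 96% |
| +0.5 | 0.07, 0.05 | 1.10 | 94% |
| +0.5 | 0.23, 0.05 | 1.17 | 92% |
| +0.5 | 0.23, 0.16 | 1.37 | 79% |
| +0.5 | 0.55, 0.16 | 1.57 | 63% |

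A correlation of −0.5 gives the mirror image, down to 0.64. The Mantel-Haenszel odds ratio stratified by centre has a median of 0.98 to 1.01 in every setting.

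**Step 3: price of stratifying.** The SD of the stratified log odds ratio is 0.31 to 0.42. Ignoring centre, 250 children per group at 10% give a standard error of √(1/25 + 1/225 + 1/25 + 1/225) = 0.298. The stratified interval is thus roughly 0.31/0.298 = 1.04 to 0.42/0.298 = 1.41 times as wide on the log scale, widest where regime is strongly centre-driven.

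**The case against.** The strongest reply is that the SAP nowhere says regimes are set by centre. Under Objective 2 it describes the oral switch as a judgement about the individual child's recovery, and [2C] adds that blood tests inform it. Naming regimes by where they were used does not make them local policy, and the remark on clustering concerns withdrawals alone. The study is also descriptive, Objective 3 plans no hypothesis test, and the odds ratios are offered as an overview.

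Much of this stands, and it rules out three stronger readings a reader might infer:

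- *The intervals are certainly too narrow.* This needs clustering of both regime and outcome, and the SAP gives no figure for either.
- *The usual cluster formula, 1 + (m − 1) × ICC(outcome), gives the size.* With m = 10 it yields 1.18, 1.45 and 1.90 for outcome ICCs of 0.02, 0.05 and 0.10. But it assumes that centre wholly fixes the regime, against the SAP's account of the switch, and it counts all cases rather than simple cases.
- *Centre differences will be reported as regime effects.* With zero centre-level correlation the crude odds ratio is unbiased.

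Nor does the SAP say that readmission or a drug change defines failure. Surgery is its only example; the longer list in [3A] is of actions taken.

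The reply does not remove the omission. No section says how centre enters [3B] or [3C], and printing a 95% CI claims a precision that the overview wording does not withdraw.

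**Conclusion.** The point holds as a gap worth closing, not as a demonstrated error. [3B] and [3C] make no allowance for centre. At 10 cases per equal-sized centre, with assumed ICCs of 0.2 to 0.5 for regime and 0.05 to 0.10 for outcome, the design effect is about 1.09 to 1.45 and coverage about 94% to 90%. It is less for simple cases only and more with unequal or larger centres. At 10 per centre of equal size it reaches 1.90 only if centre fixes the regime wholly and the outcome ICC is 0.10.

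Confounding by centre is potentially the larger problem but is conditional. At an assumed centre-level correlation of 0.5, a true odds ratio of 1 appears as 1.10 to 1.57 in the settings tabulated. The SAP offers no evidence on that correlation. The argument from thresholds for action bears on Treatment Failure alone.

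**What to change.** In [3B] and [3C], and in Tables 3B-1 and 3C-1:

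1. Keep the crude odds ratio, but compute its 95% CI with centre as the cluster.
2. Report beside it a centre-stratified odds ratio (Mantel-Haenszel or conditional). Where surgery types are too sparse, stratify by Tertiary / Secondary instead, noting that this removes only differences between centre types.
3. State which centre a transferred child counts under, since transfers between hospitals are recorded.

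Step 1 alone is not enough: cluster-robust errors change the interval and leave any centre confounding in the estimate. About 50 centre indicators in an ordinary logistic model would be unstable at about 10 cases each, and a random intercept alone does not fully remove confounding between centres.

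The cost is a little more analysis on recorded data and wider intervals, because centres where every child has the same regime, or the same outcome, add nothing to the stratified estimate. Confounding by the child's own severity remains, and the report should say so.

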Appendix A statistical analyses plan: Template Results Tables

1A: Demographics, past medical history, and presenting limbs/joints affected.

TABLE 1A-1

Demographics	Appropriate Summary Statistics
Age (years)	
Male	
Ethnicity	
European North/East/Mid	
European South (Mediterranean)	
European Roma	
African/Caribbean North African	
African/Caribbean Sub Saharan	
African/Caribbean Afro-caribbean	
Asian Indian Subcontinent	
Asian SE (Vietnam, Thailand, Indonesia, Malaysia, Phillipines)	
Asian East Asia (China, Japan, Korea)	
Asian West Asia (Afghanistan, Iranian)	
Middle Eastern Turkish	
Middle Eastern Arab peninsula	
Other/Mixed	

TABLE 1A-2

Diagnosis Group	Appropriate Summary Statistics
Simple ^(a)	
OM	
SA	
Complex ^(b)	
OM	
SA	
Presentation due to infected implant or surgery from previous orthopaedic surgery	
Misdiagnosed	
Types of diagnoses for misdiagnosed:	
Cellulitis	
Discitis	
Reactive arthritis	
Infective arthritis	
Joint effusion	
Abscess	
Other	
Unknown/Undecided	

^(a)Acute SA/OM with no co-morbidities; ^(b) 'Chronic SA/OM' or 'Acute SA/OM with co-morbidities'

TABLE 1A-3

Presentation	All	Simple (n=?)	Complex (n=?)
Presenting to:			
Outpatient Clinic			
Inpatient			
GP			
Emergency Department			
Walk-In Centre			
Not known			
Limbs/Joints affected*:			
Hip			
Shoulder			
Knee			
Ankle			
Wrist			
Skull			
Mandible			
Humerous			
Clavicle			
Radius			
Ulna			
Pelvis			
Rib			
Femur			
Tibia			

Fibia

Sternum

Elbow

Foot

Calcaneum

Lumbar vertebrae

Cervical vertebrae

Thoracic vertebrae

Sacrum vertebrae

*Categories not mutually exclusive, so more than one bone/joint can be recorded per patient.

TABLE 1A-4

History of Orthopaedic Surgery	Any	In 6 months prior to presentation (same bone/joint as at presentation)
Yes?		
Bone/joint affected*:		
Knee		
Clavicle		
Radius		
Ulna		
Humerus		
Tibia		
Femur		
Ankle		
Side:		
Right		
Left		
Both		

TABLE 1A-5

Medical History	Yes	No	Not tested / unknown
Co-morbidities indicating complex case:			
Sickle cell disease			
Known immunocompromise			
Indwelling central venous catheter or PICC			
Cystic Fibrosis			
Cerebral Palsy			

TABLE 1A-6

Medical History	Simple	Complex	Other
Other Medical Conditions:			
Congenital cardiac disease			
Diabetes Mellitus			
Purpura Fulminans			
Malnutrition			
Other			
Immune modulating treatment in last 6 calendar months?			
Steroid			
Radiotherapy			
Chemotherapy			
Azathioprine			
Cyclosporin			
Cyclophosphamide			
Rituximab			

Leflunomide

Tacrolimus

Sirolimus

Other

Infection History in the last 12
calendar months?

Pneumonia

Septicaemia

Pyelonephritis

Cellulitis / soft tissue infection

Meningitis

Osteoarticular infection

Abdominal sepsis

Varicella

Other

History of Trauma in the last
month?

Other Surgery in 12 months prior to
presentation?

Pre-presentation variables that affect drug choice, dosage and duration. (Simple cases only)

TABLE 1A-7

Antibiotic Medical History	N(%)	Route		Duration
		IV	Oral	> 1 week
Penicillin allergy		-	-	-

Antibiotics (1 month
pre-presentation)

Any

Flucloxacillin

Clindamycin

Cefuroxime

Ceftriaxone

Amoxicillin

Co-Amoxiclav

Rifampicin

Vancomycin

Fusidic Acid

Teicoplanin

Other

1B: The clinical time-line for diagnosis

TABLE 1B-1

Diagnostic and hospital stay Time-line (Days)	Appropriate Summary Statistics
From first presentation to:	
Hospital Referral	
1 st Imaging	
Pre-diagnosis surgery	
Radiological diagnosis	
Initiation of IV antibiotics	
(proxy for diagnosis of OM/SA)	

1C: Surgical procedures carried out post presentation and prior to diagnosis (before or on the same day as initiation of IV antibiotics).

TABLE 1C-1

Surgery types	Rate n (%)
Any	
Aspiration	
Incision and drainage	
Drill decompression	
Curettage/excision	
Arthrotomy	
Arthroscopy	
Amputation	

Debridement

Fasciotomy

Compartment decompression

Secondary closure

Skin graft

Other plastic surgery

1D: Summary of range of tests carried out and sensitivity of conventional microbiological tests. (Simple cases only)

TABLE 1D-1

N(%)
Children with at least one conventional test carried out
At least one micro-organism detected
Specific mirco-organisms detected by conventional testing:
Staphylococcus Aureus
PVL tested for?
Kingella Kingae
Streptococcus pyogenes
Pseudomonas
Group b Streptococcus
Salmonella
Candida
Tuberculosis
Other
PCR testing carried out

Types of sample used for conventional microbiological testing. (Simple cases only)

TABLE 1D-2

N(%)

Number of different
sample types taken

0

1

2

>2

Sample types. Children
that had at least one:

Pus (periosteal)

Bone biopsy

Pus/Wound swab

Joint aspirate

Other

1E: Blood-tests carried out at presentation. (Simple cases only)

TABLE 1E-1

Blood tests at presentation	N(%) with at least one measurement on day of presentation	Summary statistic for test results	% with elevated* results
Hb			
WCC			
N			
Plt			
CRP			
ESR			
CRP & ESR		-	-
CRP & not ESR		-	-
CRP _{max} occurring at presentation		-	-

*Above the centre specific normal range

1F: Comparing average CRP_{max} for each culture negative vs. positive, by age-group. (PCR and conventional test results combined; Simple cases only).

TABLE 1F-1

Microbe	Summary statistics for CRP _{max}					
	< 1 year		1-6 years		6-16 years	
	+ve	-ve	+ve	-ve	+ve	-ve
Staphylococcus Aureus						
Kingella Kingae						
Streptococcus pyogenes						
Pseudomonas						
Group b Streptococcus						
Salmonella						
Candida						
Tuberculosis						
Other						

1G: Imaging types routinely used to aid diagnosis (On day of or prior to initiation of IV; Simple cases only).

TABLE 1G-1

Imaging Type	N(%) with at least one image	Number (%) Abnormal
X-ray		
CT scan		
Ultrasound		
MRI		
Bonescan		

What is the range of durations of intravenous and oral antibiotics used to treat osteomyelitis?

2A: The clinical time-line for antibiotic treatment.

TABLE 2A-1

Antibiotic Treatment Time-line (Days)	Appropriate Summary Statistics
Length of time on:	
IV	
Oral ^(a)	
Total ^(b)	

^(a)Use time on oral antibiotics pre-discharge plus planned duration, as proxy for actual duration.

^(b) Length of time treated with any antibiotic (for some children oral antibiotics were given concurrently to IV. So the Total length of time is not necessarily the time on IV plus the time on Oral)

Types of antibiotic regimes experienced.

TABLE 2A-2

Antibiotic Regime	All	Centre Type	
		Tertiary	Secondary
Number of different antibiotics given at initiation of treatment			
1			
2 or more			
Timing of oral switch			
Very Early (< 1 week)	Also report median & IQR		
Early (1-2 wks)	for each category		
Standard / Late (> 2 wks)	here		

Total course of antibiotics

Shortened (< 6 weeks)

Standard (> 6 weeks)

DoseAugmented at least once^(a)

Standard throughout

**Total number of antibiotics
prescribed****IV:**

1

2

>2

Oral:

1

2

>2

^(a)At least one IV antibiotic given at a high dose

2B: IV and oral antibiotics prescribed prior to discharge.

TABLE 2B-1

Antibiotic	Given at least once	Part of initial prescription	Daily dose per kg weight of child	Frequency					Duration (> 1 week)
				6 hourly	8 hourly	12 hourly	Once daily	Other	
IV									
Flucloxacillin									
Clindamycin									
Cefuroxime									
Ceftriaxone									
Other									
Oral									
Flucloxacillin									
Clindamycin									
Amoxicillin									
Co-Amoxiclav									
Rifampicin									

Other

TABLE 2B-2

Antibiotics given as part of first treatment	Centre Type		Given had a penicillin allergy	Given had sickle cell disease
	Tertiary	Secondary		
IV				
Flucloxacillin				
Clindamycin				
Cefuroxime				
Ceftriaxone				
Other				
Oral				
Flucloxacillin				
Clindamycin				
Amoxicillin				
Co-Amoxiclav				
Rifampicin				
Other				

2C: Blood-tests carried out immediately prior to oral switch

TABLE 2C-1

Blood tests	Number (%) of cases with test results immediately prior to switch		Summary statistic for test results	As a proportion of CRP _{max}
	Tertiary	Secondary		
Hb				-
WCC				-
N				-
CRP				-
ESR				-
CRP & ESR			-	-
CRP & not ESR			-	-

2D: Surgery occurring after the initiation of IV antibiotics (post diagnosis).

TABLE 2D-1

Surgery types	Rate n (%)
All	
Aspiration	
Incision and drainage	
Drill decompression	
Curettage/excision	
Arthrotomy	
Arthroscopy	
Amputation	
Debridement	
Fasciotomy	
Compartment decompression	
Secondary closure	
Skin graft	
Other plastic surgery	

2E: Length of stay in hospital by age-group and site type.

TABLE 2E-1

Centre type	Age group			
	All	< 1 year	1-6 years	6-16 years
All				

Tertiary

Secondary

2F: Imaging types routinely used post diagnosis.

TABLE 2F-1

Imaging Type	Number (%) of cases imaged at least once post-diagnosis		Number (%) Abnormal
	Tertiary	Secondary	
X-ray			
CT scan			
Ultrasound			
MRI			
Bonescan			

2G: Antibiotic regimes prescribed at discharge. As part of this – what percentage went home on IV as opposed to oral antibiotics.

TABLE 2G-1

Antibiotic	N(%)	Daily dose per kg weight of child	Planned Duration
Went home on			
IV		-	-
Oral		-	-
IV			
Flucloxacillin			
Cefuroxime			
Ceftriaxone			
Benzyl Penicillin			
Other			
Oral			
Flucloxacillin			
Cefalexin			
Co-Amoxiclav			
Other			

2H: Were discharge antibiotic regimes adhered to? Percentages of treatments shortened or changed post discharge, split by who made the decision: parent, hospital or GP. What were the main reasons for non-adherence or change of regime post discharge?

TABLE 2H-1

Adherence to prescribed antibiotic regimes	Number (%)
Stopped early by:	

Parent
Hospital

GP

Changed by:

Hospital

GP

Reason for shortening / change of
regime:

Unpalatable antibiotic

Diarrhoea

Rash

Resolution of symptoms

Recurrence of infection

3A: Complication types by action taken.

TABLE 3A-1

Complication	N (%)	Action taken				
		None	Surgery	Change of antibiotic regime	Re-admission to hospital	Other action
Any Complications						
Complication type:						
Fever						
Recurrence of						
Infection						
Dislocation						
Subluxation						
Pathological						
Fracture						
Sinus						
Other						

3B: Treatment failures and complications by type of antibiotic regime.

TABLE 3B-1

Antibiotic Regime	Treatment Failure?			Any complication?		
	Yes	No	Odds ratio	Yes	No	Odds Ratio
Timing of oral switch						
Early (< 2 weeks)						
Standard / Late (> 2 wks)						
Total course of antibiotics						

Shortened (< 6 weeks)

Standard (> 6 weeks)

Dose Repeated for IV
and oral separately

High

Majority Lower range

3C: Treatment failures and complications by type of surgery.

TABLE 3C-1

Surgery	Treatment Failure?			Any complication?		
	Yes	No	Odds ratio	Yes	No	Odds Ratio
Surgery undertaken after date of 1 st presentation						
Aspiration						
Incision and drainage						
Drill decompression						
Curettage/excision						
Arthrotomy						
Arthroscopy						
Amputation						
Debridement						
Fasciotomy						
Compartment decompression						
Secondary closure						
Skin graft						
Other plastic surgery
